7.0 PATIENT MATERIALS

7.1 Instructional materials

Subjects will receive a pamphlet outlining the steps of the program for quick, accurate and discrete reference after they receive in-person instruction.

7.2 Program materials

Subjects will receive personal lubricant in sufficient quantity to perform the program per protocol for 12 weeks. They will also receive the FeMani Vibrating Massage Wand free of charge. This a class 1 durable medical device approved by the FDA.

7.3 Log materials

Subjects will receive a logbook and will be asked to record the amount of times they perform both the internal and external portions of the VRP on a weekly basis as well as number of times they did not take their Aromatase Inhibitor.

8.0 TREATMENT COMPLIANCE

8.1 Assessment of Treatment Compliance

A member of the study team will contact subjects at 1-2 weeks and 1 month (+/- 1 week) after baseline VRP instruction to assess adherence to the program, to remind the subject to log adherence to the VRP, to remind the subjects to document when they take their AI, to answer any questions regarding the program, and to offer any additional instructions regarding the program. The preferred contact will be phone-based.

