2.4 Exploratory Objectives

2.4.1 To assess percentage of subjects who adhere at least 90% to AI therapy throughout the course of the study.

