8.2 Subject replacement

For this study, lack of adherence will be defined as < 3 days/week participation for 2 weeks or

more as assessed on the 1-month phone call. If a subject is found to be not adhering to the study protocol, a new subject will be enrolled in a 1:1 ratio. Subjects lost to follow-up for any reason will be replaced in a 1:1 ratio. All subjects enrolled and not lost to follow-up, regardless of adherence status, will have their data collected and analyzed accordingly.

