9.3 Logbooks

The logbooks will be provided to subjects at the baseline visit. We will ask the subject to enter the days they have performed the VRP program during the study. They will also be asked to record the number of days of each week that they did not take their Aromatase Inhibitor. Subjects will be reminded to enter data into this log with phone calls approximately 1 week and approximately 1 month after VRP instruction. Logbooks will be collected from subjects at the study completion visit.

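### The reminder calls and the logbook word the AI item in opposite directions, log units differ between sections, and blank weeks have no rule, so the exploratory 90% AI adherence result can be misclassified

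*Combined protocol and SAP*

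**What the plan says.** The exploratory objective in Section 2.4 is "To assess percentage of subjects who adhere at least 90% to AI therapy throughout the course of the study". Sections 3.0 and 11.6 name a patient-reported log as the source. Neither gives a formula, a denominator or a rule for blank entries, and no pill count, refill record or other cross-check is described.

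Three sections describe what subjects are told to record about the AI:

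- Section 8.1, reminder calls: "to remind the subjects to document when they take their AI".
- Section 7.3, logbook content: VRP use "as well as number of times they did not take their Aromatase Inhibitor".
- Section 9.3, logbook content: "record the number of days of each week that they did not take their Aromatase Inhibitor".

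Two sections describe what they record about the VRP:

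- Section 7.3: "record the amount of times they perform both the internal and external portions of the VRP on a weekly basis".
- Section 9.3: "enter the days they have performed the VRP program during the study", with no split by portion.

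The plan's only definition of VRP non-adherence is in Section 8.2: "lack of adherence will be defined as < 3 days/week participation for 2 weeks" or longer, judged at the 1-month call. Logbooks are handed in once, at the completion visit (Section 9.3 and Appendix 1).

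**The concern.** The reminder points subjects to doses taken and the log asks for doses not taken. Section 3.0 gives the calls the job of sorting out problems with logging, so the contact meant to correct errors carries wording that differs from the form. The two descriptions of the log also differ in unit for both the AI (times, days) and the VRP (times per portion, days).

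A further weakness comes with recording only what was missed. A subject who missed nothing has little to write, and a subject who stopped filling in the log writes nothing either. Unless a zero must be entered, the two look the same. Because the book comes back only at the end, an unclear entry can then be clarified only from memory.

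At stake is the one AI adherence result the trial will produce. AI non-adherence is part of the trial's stated motivation in Section 1.0, but the objective is exploratory.

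**Working it through.** The plan states no figure for this point, so there is none to reproduce. The check compares the wording and then works out how much ambiguity the 90% threshold can absorb.

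**Wording side by side**

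| Item | 7.3 | 8.1 | 9.3 | 8.2 rule |
|---|---|---|---|---|
| AI | times not taken | when taken | days per week not taken | not used |
| VRP | times, internal and external portions | no unit given | days, portions not separated | days per week |

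For the AI, the direction differs between 8.1 and the two log sections, and the unit differs between 7.3 and 9.3. For the VRP, the unit differs between 7.3 and 9.3.

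**Missed days allowed at 90%**

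Inputs: the 90% threshold (2.4.1) and a completion visit at 12 weeks ± 4 weeks (9.4). Assumption: one AI dose per day, since the documents give no dosing frequency. Formula: the largest m with (D − m)/D ≥ 0.90.

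- D = 56 days (week 8): m = 5, since 51/56 = 91.1% and 50/56 = 89.3%.
- D = 84 days (week 12): m = 8, since 76/84 = 90.5% and 75/84 = 89.3%.
- D = 112 days (week 16): m = 11, since 101/112 = 90.2% and 100/112 = 89.3%.

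**Blank weeks**

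Take a subject with every logged day taken and some weeks blank, over 84 days.

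- One blank week: adherence lies between 77/84 = 91.7% and 84/84 = 100%. She is adherent either way.
- Two blank weeks: between 70/84 = 83.3% and 84/84 = 100%. The 90% line falls inside this range, so her class is unknown.

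Dividing by logged days only would not solve this. It gives 70/70 = 100% for the second subject even if all 14 unlogged days were missed and true adherence was 83.3%.

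**Direction of the entry**

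A weekly entry of 1 means 6/7 = 85.7% if it counts days missed and 1/7 = 14.3% if it counts days taken. At the extreme, an entry of 7 meant as taken but read as missed turns 100% into 0% for that week.

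**Effect on the reported proportion**

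Each misclassified participant moves it by 1/25 = 4 points at the full sample, or 1/15 = 6.7 points if the trial stops after stage 1. Section 8.2 replaces some participants while still analysing their data, so the denominator could exceed 25 and the step would then be slightly smaller.

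**VRP unit**

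Both portions done on the same 3 days could be recorded as 3 + 3 = 6 times or as 3 days. If the portions are summed, 4 times could be 2 days. A count of times therefore cannot be converted to days per week without a further assumption.

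**The case against.** The strongest reply is that 7.3 and 9.3, the two sections that define the log, agree on direction: both record what was not taken. Section 8.1 defines no data field, and 9.3 describes the same calls simply as reminders to fill in the log. The printed form decides what is entered. It is not in the documents and may be perfectly clear. This stands as a limit on likelihood. A reader might infer that adherence will be wholly reversed, but that needs a subject to enter days taken, week after week, in a field defined as days missed, with nobody noticing. It is a worst case. What remains is that 8.1 conflicts with 7.3 and 9.3 whatever the form says.

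A reader might also infer that the plan scores a blank week as full adherence. No section says so. The documents support only the narrower statement that there is no scoring rule and that a missed-dose log cannot distinguish the two cases without a required entry.

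A third tempting inference is that the times/days mismatch decides who counts as non-adherent under 8.2. That rule is judged at the 1-month call, well before the logbook is collected, and nothing says subjects read from the log during the call. Section 8.2 also keeps non-adherent subjects in the analysis unless they are lost to follow-up.

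Finally, the two-blank-weeks example does not say how often this will happen, and the documents give no basis for a rate. It shows only that an ordinary lapse in logging is large enough to matter at a 90% threshold.

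**Conclusion.** The inconsistency is in the current text and should be removed. The AI item has one direction in 8.1 and the other in 7.3 and 9.3, with two units in the log sections. VRP use is in times per portion in one place and days in another. Nothing tells the analyst how to treat a blank week.

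The consequence is possible misclassification in one exploratory, descriptive result. With one dose a day, the margin at 90% is 8 missed days in 84 (5 in 56, 11 in 112), and each participant placed in the wrong class shifts the proportion by 4 points at n=25. How many would be affected cannot be estimated from the documents.

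The cytology response, the Simon stopping and rejection rule and the phone-assessed rule in 8.2 do not use the log, so this is no threat to the trial's main conclusion. It is worth acting on because the log is the only source for the objective and the remedy is nearly free.

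**What to change.** **Sections 7.3, 8.1 and 9.3 and the logbook form.** Use one AI item everywhere: number of days the AI was taken this week, 0-7, with an entry required every week, including 0. Word the reminder call to match. Log VRP use as days per week, separately for the internal and external portions, so that the record is in the same unit as 8.2. The 8.2 assessment itself need not change.

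**Section 11.6.** State the calculation:

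- The denominator is all days from VRP instruction to the completion visit.
- Blank weeks are missing, are not counted as adherent, and stay in the denominator.
- Report the proportion at or above 90% as two bounds: all blank days taken, and all blank days missed.
- Report the number of incomplete logs.

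For the subject with two blank weeks above, this gives 83.3% to 100% and shows openly that her class is undetermined.

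The cost is minor wording in the sections named, one edit to the form before use, and one extra descriptive line in the results. No visits, staff or measurements are added.

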8.2 Subject replacement

For this study, lack of adherence will be defined as < 3 days/week participation for 2 weeks or

more as assessed on the 1-month phone call. If a subject is found to be not adhering to the study protocol, a new subject will be enrolled in a 1:1 ratio. Subjects lost to follow-up for any reason will be replaced in a 1:1 ratio. All subjects enrolled and not lost to follow-up, regardless of adherence status, will have their data collected and analyzed accordingly.

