9.2.1 Post-intervention cytology collections

A clinician trained in the collection of lower female genital tract cytology specimens will collect the cytology. The amount collected will be equivalent to a routine PAP test. The cytology specimen will be transported to the pathology department and stored as documented in **Section 9.1.1**. At the completion of each stage of the study, all pre-intervention cytology collections and post-intervention cytology collections will be pooled and interpreted with the specimens blinded as to the timing of the collections.

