11.2 Sample Size Determination

The Simon Two Stage design will be utilized for this study. The null hypothesis that the true positive response rate is 10% will be tested against a one-sided alternative using the exact binomial test. The study will be powered to detect a positive response rate of 30% or greater with approximately 80% power and a type I error rate of 5%.

The first stage sample size will be 15 patients. If there are 1 or fewer responses in these 15 patients, the study will be terminated. If the trial goes on to the second stage, a total of 25 patients will be studied (i.e. additional 10 patients will be recruited). The null hypothesis will be rejected if 6 or more responses are observed in 25 patients. We will assess response with a blinded standardized interpretation of superficial vaginal epithelial cells by a board-certified pathologist.

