12.0 SUBJECT COMPLETION/WITHDRAWAL

12.1 Completion

A subject will be considered to have completed the study if she returns for the 12-week study completion visit.

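### Sections 8.2 and 11.2 conflict: women labelled non-adherent are replaced 1:1 yet still analysed, while the decision rule exists only for 15 and 25 patients

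*Combined protocol and SAP*

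**What the plan says.** Section 8.2 (Subject replacement) defines lack of adherence as under 3 days a week for two weeks or "more as assessed on the 1-month phone call". It then gives two instructions:

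- On enrolment: "If a subject is found to be not adhering to the study protocol, a new subject will be enrolled in a 1:1 ratio".
- On analysis: "All subjects enrolled and not lost to follow-up, regardless of adherence status, will have their data collected and analyzed accordingly".

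Section 12.1 treats a low user who comes back as a completer: "A subject will be considered to have completed the study if she returns for the 12-week study completion visit".

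Section 11.2 (Sample Size Determination) fixes the numbers. For stage 1: "If there are 1 or fewer responses in these 15 patients, the study will be terminated". For the total: "If the trial goes on to the second stage, a total of 25 patients will be studied". For the final test: "The null hypothesis will be rejected if 6 or more responses are observed in 25 patients". It gives no cut-off for any other number and does not say who fills the 15 or the 25 once replacements exist.

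Section 9.2.1 ties slide reading to the stages: "At the completion of each stage of the study, all pre-intervention cytology collections and post-intervention cytology collections will be pooled and interpreted". It does not say whether stage 1 ends at 15 women or at 15 plus their replacements.

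**The concern.** A replacement for a woman lost to follow-up does not change the analysed number, because the lost woman is not analysed. A replacement for a non-adherent woman does change it, because both women are analysed. With k such women who return at 12 weeks, section 8.2 leads to 25+k analysed women and section 11.2 has no rule for them.

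The primary conclusion is a responder count set against a fixed number of women, so the choice can decide the result. Take 28 analysed women with six responders, one of them among the three women outside the chosen 25. Six among all 28 rejects the null if the cut-off is left at 6; five among the 25 does not. If the choice is made after slides are read, it can depend on the data. The same gap affects the stage-1 stopping decision.

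**Working it through.** **Inputs.** From section 11.2: null rate 10%, alternative 30%, one-sided exact binomial test, type I error 5%, power about 80%, 15 then 10 women, stop at 1 or fewer, reject at 6 or more. From section 8.2: 1:1 replacement, with everyone not lost to follow-up analysed. The number k is not given and is varied.

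**Formula.** With k1 extra women in stage 1, k2 in stage 2 (k1 + k2 = k) and cut-off c:

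P(reject) = Σ over x ≥ 2 of P[Bin(15+k1, p) = x] × P[Bin(10+k2, p) ≥ c − x].

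**The plan's own design (k=0, c=6, p=0.10).**

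- x=2: 0.2669 × 0.0128 = 0.00341
- x=3: 0.1285 × 0.0702 = 0.00902
- x=4: 0.0428 × 0.2639 = 0.01130
- x=5: 0.01047 × 0.6513 = 0.00682
- x≥6: 0.00225

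The sum is 0.0328. The same sum at p=0.30 gives 0.8017. The stated design therefore reproduces: type I error 3.28%, power 80.2%.

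**Three extra women in stage 2, cut-off still 6.** The stage-2 tails now come from 13 women: 0.0342, 0.1339, 0.3787 and 0.7458. The terms are 0.00912 + 0.01720 + 0.01622 + 0.00781 + 0.00225 = 0.0526.

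**Other values of k.** Ranges run over the stage in which the extra women fall. All women share the same response rate.

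| k | Women analysed | Type I error, cut-off kept at 6 | Cut-off tied to number | Type I error with it | Power at 30% with it |
|---|---|---|---|---|---|
| 0 | 25 | 3.28% | 6 | 3.28% | 80.2% |
| 1 | 26 | 3.89%–3.93% | 6 | 3.89%–3.93% | 83.1%–83.4% |
| 2 | 27 | 4.55%–4.65% | 6 | 4.55%–4.65% | 85.5%–86.2% |
| 3 | 28 | 5.26%–5.45% | 7 | 1.76%–1.79% | 77.4%–77.9% |
| 4 | 29 | 6.02%–6.32% | 7 | 2.11%–2.16% | 80.5%–81.2% |
| 5 | 30 | 6.84%–7.27% | 7 | 2.50%–2.58% | 83.1%–84.0% |
| 8 | 33 | 9.51%–10.57% | 7 | 3.93%–4.17% | 89.0%–90.5% |

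**Stage-1 stopping under the null.** With 15 women: 0.9^15 + 15 × 0.1 × 0.9^14 = 0.2059 + 0.3432 = 0.549. With 18 women: 0.9^18 + 18 × 0.1 × 0.9^17 = 0.1501 + 0.3002 = 0.450.

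**If non-adherent women respond less often under the null.** Put the k extra women in stage 2 at 5% and the other 25 at 10%, so the stage-2 count is Bin(10, 0.10) + Bin(k, 0.05). With cut-off 6, type I error is 4.23% at k=3 and 4.93% at k=5. With the extra women in stage 1 instead, it is 4.31% and 5.09%.

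**How large k might be (assumed rates).** Suppose each enrolled woman, replacements included, has probability q of being labelled non-adherent, and all who are labelled return. Then P(k ≥ 3) = 1 − (1−q)^25 × (1 + 25q + 325q²). This is about 15% at q=5%, 52% at q=10% and 93% at q=20%.

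**The case against.** The best reply is that a replacement ordinarily takes the replaced subject's place, and that section 11.2 speaks of 25 patients in total. Non-adherent women would then be reported outside the primary 25, and type I error would stay at 3.28%. Part of this stands: inflation needs the team to apply 6 to more than 25 women, which departs from 11.2. But no section says that the labelled women are set aside, and a primary set of adherent women only would contradict the second instruction in 8.2.

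The reply also notes that the excess at k=3 is under half a percentage point, that k of 1 or 2 stays within 5%, that two adherence contacts are planned, and that non-users may respond at less than 10%. All of this stands and limits the size of the problem. It does not say which women are counted.

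A reader might infer more than the documents support in two ways. One is that the trial's type I error exceeds 5%. That cannot be said without a non-adherence rate, and it depends on keeping 6 for more than 25 women. The other is that section 12.2 withdraws low users and so flatly contradicts 8.2. Section 12.2 refers to adherence to study procedures, and 9.1, under that title, covers evaluations and data collection. The withdrawal reason may therefore concern missed evaluations only. It is an ambiguity worth removing and adds no weight to the main point.

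**Conclusion.** The point holds as a conflict between stated rules: following 8.2 gives 25+k analysed women, and 11.2 has no rule for that number. The primary set and the close of stage 1 are undefined from the first labelled woman who returns.

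The numerical harm is conditional. If all women are counted with the cut-off at 6 and a common 10% null rate, type I error passes 5% only from k=3 (5.26%–5.45%) and reaches 6.84%–7.27% at k=5. If non-adherent women respond at 5% and fall in stage 2, the limit still holds at k=5 (4.93%). The size of k is an assumption throughout. The plan should be amended because the gap lies in the primary decision rule and can be closed with wording alone.

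**What to change.** Before any stage-1 slide is read:

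- **Section 11.2:** state that all women analysed under 8.2 count towards the primary test. Stage 1 closes when the 15 and their replacements have finished, with the stop still at 1 or fewer responses. The final cut-off follows the number analysed: 6 for 25 to 27 women (type I error at most 4.7%) and 7 for 28 to 33 (at most 4.2%). If more are possible, 7 still holds at 34 (4.48%–4.81%), and 8 is needed at 35 (1.91%–2.00%).
- **Section 12.2:** state that low VRP use is not a reason for withdrawal.

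This keeps 8.2 intact and needs no new visits. It has three costs:

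- Power at exactly 28 women is 77.4%–77.9%, slightly below the target.
- Extra women in stage 1 make early stopping under the null less likely: 54.9% falls to 45.0% with three.
- The power figures assume equal response rates. If three non-adherent women respond at 10% and the other 25 at 30% (for example a stage-2 count of Bin(10, 0.30) + Bin(3, 0.10)), power with cut-off 7 is 70.0%–70.1%.

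The sponsor could instead end replacement for non-adherence and use the first 15, then 25, women not lost to follow-up. That is a design option and not a required correction, and it also costs power. With 10% of women non-adherent and responding at 10%, the mean rate is 0.9 × 0.30 + 0.1 × 0.10 = 0.28 and power is 74%. With 20% non-adherent the rate is 0.26 and power is 66%. A pre-set 15 then 15 women with cut-off 7 has type I error 2.5% and power 83%, or 77% and 69% under the same dilution, for five more women.

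Neither route settles how unreadable slides or withdrawal of consent are handled; the new wording should cover both.

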9.0 STUDY EVALUATIONS

9.1. Study Procedures

The Schedule of Events summarizes the timing of evaluations and data collection (**Appendix 1**). Baseline PRO assessments should be conducted after eligibility is verified and before any tests, procedures, or trainings to prevent influencing subject perceptions.

9.1.1 Pre-intervention cytology collections

A clinician trained in the collection of lower female genital tract cytology specimens will collect the vaginal cell cytology. The collection is done in a process similar to a routine PAP test. A swab is placed into the vagina and is wiped against the vaginal wall to collect cells and fluids. The amount collected will be equivalent to a routine PAP test. The cytology specimen will be transported to the pathology department inside a Biohazard bag inside an opaque sealed envelope. The specimen will be prepared by standard cytology techniques. Slides will be housed in a UWCCC research office.

At the end of the study, slides will be randomly labeled and organized such that it is impossible to identify timing of collection, or even if the slides are associated with the same participant. Following this blinding, all slides will be interpreted by a trained cytopathologist and destroyed after final study analysis.

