3.0 STUDY DESIGN OVERVIEW & RATIONALE

We will utilize a prospective Simon two-stage Phase II study design. Breast cancer patients who have completed primary active therapy for breast cancer (e.g. surgery, chemotherapy and/or radiation) and are currently taking maintenance aromatase inhibitors (AIs) such as anastrozole, letrozole or exemestane will be approached. We will assess response to the VRP with a blinded standardized interpretation of superficial vaginal epithelial cells. Entrance criteria will stipulate baseline measurements must be < 2%. If the subject has $\geq 4\%$ superficial vaginal cells on cytologic evaluation after the intervention period, then the response will be considered positive.

After documentation of eligibility according to the inclusion and exclusion criteria (**see Section 5.0**) and after enrollment, the subject will receive instruction in the VRP (**see Section 6.0** for details and **Study Schema**). Baseline demographic data, baseline vaginal cell cytology, vaginal pH, and PROs will be collected prior to initiating the VRP instruction. During the time on study, subjects will log their adherence to the prescribed therapy schedule of the VRP and AI therapy. Subjects will receive reminder contacts from study staff/team member 1 week and 1 month after initial instruction. These calls will function to ensure that subjects have had adequate instruction, and problem-shoot any issues with adherence to the program and logging adherence. The subject will return the journal at the 12-week study completion visit when vaginal cell cytology, vaginal pH, and PROs will be assessed.

The primary endpoint of percent superficial vaginal cells will be determined via blinded review by a board-certified pathologist experienced with interpretation of cytology. Secondary endpoints of pH will be logged at the time of the exams and PROs will be determined by standardized, validated scoring metrics for the respective PRO measures used. The exploratory analysis of AI adherence will be determined using patient-reported logs.

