4.2 Recruitment

Subjects will be recruited with the assistance of the UWCCC research staff..

To increase accrual, the research staff will employ the following strategies:

- 1) Study staff will identify current patients with Stage 0-3 breast cancer who are receiving aromatase inhibitors (anastrozole, letrozole or exemestane). Study staff will focus on patients who have upcoming follow-up visits at the UW.
- 2) Identified patients may be sent a letter or a MyChart message briefly describing the study (see script in Appendix 2)
- 3) Patients who receive the letter or message will be asked in the letter or message to contact the research staff via phone or email within a 7-day time-frame if they **do not wish** to be approached with information about the study (“opt-out”).
- 4) Research staff will contact patients who do not opt-out. Research staff will attempt to contact patients, via phone, up to 3 times over the course of 2-3 weeks to discuss

their interest in learning about the study. At the time of the phone call, patients may decline this conversation if they are not interested in the study. See script in Appendix 3.

- 5) For patients that staff are not able to contact or who wish to delay the conversation, the research staff will notify the treating physicians to discuss the study further at the time of the clinic visit.
- 6) For interested patients, research staff will review the trial by phone or in person. With the patient's permission, research staff may ask questions related to medications, recent surgery or anti-cancer therapies and menopausal status to determine gross eligibility.
- 7) To obtain final consent, enroll subjects into the study and complete baseline evaluations, research staff will employ a standard opt-in approach. This would be scheduled at a time convenient to the patient, and would likely coincide with a scheduled clinical follow-up visit. This would reduce the participation burden for interested patients.
- 8) Patients may also be approached by a member of their clinical team when present for a routine clinic visit. The clinic team member will introduce the study to potentially eligible patients. If the patient is interested in learning more about the study, a member of the research team will review the study details and continue with the informed consent process.

4.3 Consented subjects will be registered to the study using the OnCore database by study staff.

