5.0 SUBJECT ELIGIBILITY

5.1. Inclusion Criteria

Each potential subject must satisfy all of the following criteria to be enrolled in the study:

_____ **5.1.1** Females \geq age 18 diagnosed with Stage 0-3 breast cancer

_____ **5.1.2** Have completed active primary treatment

- Defined as surgery, chemotherapy and/or radiation for the treatment of breast cancer
- Does not include immunotherapy or other targeted therapies such as trastuzumab, CDK 4/6 or mTOR inhibitors

_____ **5.1.3** Have been receiving AIs for at least 6 months prior to enrollment

_____ **5.1.4** Plan to continue AIs for an additional 3 months

_____ **5.1.5** Amenorrhea for at least 12 months at enrollment regardless of cause

_____ **5.1.6** Participants must be able to read and write in English

_____ **5.1.7** Participants must have < 2% superficial vaginal cells on cytologic evaluation

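### No described slide reading comes before VRP instruction, so the <2% entry criterion (5.1.7) cannot be applied as written; and 9.1.1 contradicts 9.2.1, the only section whose reading time serves the stage 1 rule

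*Combined protocol and SAP*

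**What the plan says.** **Entry.** The inclusion criteria (5.1) open with "Each potential subject must satisfy all of the following criteria to be enrolled in the study", and item 5.1.7 reads "Participants must have < 2% superficial vaginal cells on cytologic evaluation". Section 3.0 repeats the criterion and gives the order of events: "After documentation of eligibility according to the inclusion and exclusion criteria", and after enrolment, the woman is taught the VRP.

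**Before the visit.** The contact described in 4.2 is a coarse screen: "research staff may ask questions related to medications, recent surgery or anti-cancer therapies and menopausal status to determine gross eligibility". Cytology is not part of it.

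**Collection and reading.** Appendix 1 schedules the baseline swab at enrolment, and its footnote A allows enrolment and VRP instruction to take place together. Under 9.1.1 the specimen goes to the pathology department for preparation, and then "Slides will be housed in a UWCCC research office". The section continues "At the end of the study, slides will be randomly labeled and organized such that it is impossible to identify timing of collection", and "Following this blinding, all slides will be interpreted by a trained cytopathologist and destroyed after final study analysis". Section 9.2.1 gives a different time: pre- and post-intervention slides are pooled and read, blinded to timing, on completion of each stage.

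**Use of the result.** Section 11.2 stops the trial if at most 1 of the first 15 women responds. Otherwise it continues to 25 and rejects the null with 6 or more responses. Section 10.1 defines response as a change from below 2% to at least 4%. Section 11.3 states only the post-intervention condition of at least 4%.

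**The concern.** An entry criterion works only if its result is known before entry. Here the result that decides eligibility is first produced, on the described schedule, after the 12-week programme. A woman with a baseline of 2% or more could be enrolled, treated and followed before anyone knew that she did not qualify. Section 8.2 provides replacement only for non-adherence and loss to follow-up, so how to count her would be decided with outcomes in hand.

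The second issue is the interim decision. The stage 1 rule needs response counts from the first 15 women before stage 2 begins. Two sections give incompatible reading times, and one of them would leave the rule without data.

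**Working it through.** **1. Can any described reading apply 5.1.7?**

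| Step | Source | Timing relative to VRP instruction | Gives a cytology result? |
|---|---|---|---|
| Phone or in-person screen | 4.2 | Before | No |
| Baseline swab, eligibility checklist | Appendix 1 | Before, possibly the same visit | Collection only |
| Pooled blinded reading, end of each stage | 9.2.1 | After that stage's women have finished | Yes |
| Blinded reading of all slides, end of study | 9.1.1 | After all women have finished | Yes |

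No row combines a time before instruction with a result.

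A related ordering problem follows. Section 9.1 wants baseline PROs after eligibility is verified but before any test. That cannot be done when eligibility itself depends on a swab. Section 9.1.3 and Appendix 1, which place PROs at the instruction visit before the teaching, are workable.

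**2. Reproduce the plan's design.** Inputs from 11.2: null rate 10%, alternative 30%, n1 = 15 (stop at 1 or fewer), n = 25 (reject at 6 or more).

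P(reject) = Σ over x = 2 to 15 of P(X1 = x) × P(X2 ≥ 6 − x), with X1 ~ Bin(15, p) and X2 ~ Bin(10, p).

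- p = 0.10: 0.0328
- p = 0.30: 0.8017

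This agrees with the stated limit of 5% and power of about 80%.

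**3. What the stage 1 reading buys.** P(stop at 15) = (1 − p)^15 + 15p(1 − p)^14.

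- p = 0.10: 0.2059 + 0.3432 = 0.5490
- p = 0.30: 0.0047 + 0.0305 = 0.0353

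Expected size at the null = 15 + 10 × (1 − 0.5490) = 19.5.

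**4. If slides were read only at study end.** The rule becomes a single stage, P(X ≥ 6) with X ~ Bin(25, p).

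- p = 0.10: 0.0334
- p = 0.30: 0.8065
- Size: always 25

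**5. Illustration only: the criterion is not applied before treatment.** The documents give no share of women with a baseline of 2% or more, so the shares below are assumed. They show sensitivity, not prevalence.

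- *Section 10.1, ineligible women kept in the denominator and unable to respond:* p = 0.30 × (1 − x). Shares of 1%, 2%, 5% and 10% give power of 79.3%, 78.3%, 75.4% and 69.9%.
- *Section 11.3 read alone, a share x with an unchanged baseline of at least 4%:* p = x + (1 − x) × 0.10. Shares of 1% and 2% give type I error of 4.7% and 6.5%. It passes 5% at about 1.2%.

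If 5.1.7 is applied before instruction and the screening and blinded readings agree, every treated woman starts below 2%. Sections 10.1 and 11.3 then classify everyone alike, and the figures in step 2 stand.

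**The case against.** The strongest reply is that an eligibility reading is implied. Item 5.1.7 is an entry item, Appendix 1 puts the eligibility checklist and the swab in the enrolment column, the specimen goes to a pathology department, and footnote A permits a combined visit without requiring one. Nothing forbids an early reading. That is fair as far as it goes, and such a reading may be intended. But 9.1.1 does more than stay silent: it assigns interpretation of all slides to a time after the end-of-study blinding and stores them in a research office until then. Someone following that text would have no result at enrolment.

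The second reply is that the interim is provided for. This largely stands. A reader of 9.1.1 might infer that the plan has no stage 1 reading at all; 9.2.1 shows otherwise. The defect is a contradiction between two sections, and its harm arises only if 9.1.1 is the one followed.

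Third, a reader might take 10.1 and 11.3 as two rival primary endpoints. They are not, provided the entry criterion works. Section 3.0 also states the below-2% criterion immediately before its 4% rule. The difference matters only as a consequence of the missing eligibility reading.

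**Conclusion.** This is an internal inconsistency that must be fixed. It rests mainly on the entry criterion: no described step gives staff a cytology result before VRP instruction, so 5.1.7 and 3.0 cannot be carried out together with 9.1.1 and 9.2.1 as written. This conclusion comes from the text and needs no assumption.

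The conflict over reading time is a separate and smaller matter. Following 9.1.1 would cost the futility stop: a 54.9% chance of ending at 15 women when the true rate is 10%, and up to ten more women in an ineffective programme. It would cost almost nothing in error rates.

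Two stronger conclusions are not supported. The sample size is not wrong; 15/25 with these cut-offs does what 11.2 says. Nor can one conclude that type I error is inflated or power lost in this trial, because that depends on shares of ineligible women that the documents do not give.

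**What to change.** 1. **Eligibility reading.** In 9.1.1, state that the existing pathology service reads each baseline slide for 5.1.7 before VRP instruction, and that this result is withheld from the later blinded reading. Reconcile footnote A of Appendix 1 with this, and reword 9.1 so that the eligibility swab is exempt from the rule that PROs precede any test.
2. **Stage-end reading.** In 9.1.1, replace the end-of-study timing with the pooled, blinded, stage-end reading of 9.2.1, so that the rule in 11.2 can operate.
3. **One responder wording.** Use the same definition in 10.1 and 11.3. Say in advance whether the screening reading or the blinded baseline reading supplies the below-2% condition, and report the other as a sensitivity analysis. Either choice is defensible. The screening reading matches the entry decision but is not blinded to timing. The blinded reading keeps the masking but loses power where the two disagree (75% or 70% if an assumed 5% or 10% of eligible women re-read at 2% or more, by the first formula in step 5).

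Items 1 and 2 are the essential ones. Sample size and cut-offs do not change.

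**Cost.** A protocol amendment, an early reading of each baseline slide, some screen failures, and possibly a separate instruction visit, which works against the aim in 4.2 of limiting visits. A screen failure also tells a woman something about her result, so the statement in 15.5.4 that results are not released needs adjusting.
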